Cover Page

Project RESIST: Evaluating the Effects of Anti-smoking Inoculation Messages Among Young Adult Sexual Minority Women

NCT05499520

Date July 5 2024

PROTOCOL TITLE: Project RESIST: Evaluating the Effects of Anti-smoking Inoculation Messages Among Young Adult Sexual Minority Women

Brief Background

This study is the second of two randomized controlled experiments within Project Resist. The first randomized controlled experiment evaluated the effects of LGBTQ-tailoring (using a campaign logo with LGBTQ+ Pride colors and a slogan indicating the campaign's focus is LGBTQ+ health) vs. a control condition (yellow campaign logo and a slogan indicating the campaign's focus is on health in general) on intentions to quit smoking (among current smokers only), intentions to purchase cigarettes, marketing receptivity, industry beliefs, and industry attitudes (both current and non-current smokers). The messages used highlighted anti-tobacco industry arguments (e.g., how the tobacco industry targets children) and health impacts of cigarette smoking (e.g., risks of smoking related illnesses). Results from this experiment have been reported ([NCT04812795](#) and [publication](#)).

In this experiment, we conducted a national online survey experiment among young adult cisgender and transgender SMW smokers and non-smokers to evaluate the effects of exposure to anti-tobacco-industry inoculation health messages that are tailored for LGBTQ+ audiences. We varied the dose (3 messages vs. single message vs. no message), latency (immediate vs. 1-week delay and 1-month delay), and boosters (3 weekly boosters vs. a single dose) of anti-smoking messages on smoking and quitting intentions. Participants were randomized to one of 9 experimental arms using a fractional factorial design. All messages used LGBTQ+ tailored messages and highlighted anti-tobacco industry arguments. Six of the 12 messages used were identical to those used in the first experiment described above and six messages were new messages that were created.

Study Hypotheses

We hypothesize that multiple exposures (3 vs. single), delayed exposure (1-week or 1-month vs. immediate), and booster exposures (3 boosters vs. none) of anti-tobacco industry inoculation health messages will be associated with increased resistance to marketing, reduced smoking susceptibility, reduced intention to purchase cigarettes, and increased quitting intention.

Sample Enrollment

[figure not shown]

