This study recruited young adult sexual minority women (SMW), ages 18-30 years, those who current smoke ($n = 1075$) and those who did not smoke ($n = 1516$). Participants were recruited through a combination of the Prolific online panel (~62% of the sample), The Population Research in Identity and Disparities for Equality (PRIDE) Study (~13%), social media advertising (paid Instagram ads and posting through LGBTQ+-serving community organizations' social media accounts) (~14%), and a dating app (HER) (~11%). Participants were asked to complete a baseline survey and then randomized to one of the 9 message conditions (see Experimental conditions table below). **Figure 1** summarizes the CONSORT flow diagram.

Our planned targeted enrollment was to recruit 1500 participants who currently smoke and 1500 who did not currently smoke (total $n=3000$). We used GPower (ver. 3) to estimate the effect sizes in the outcome variables as a function of message condition, assuming two-tailed tests, with 80% power and $\alpha=0.05$, and factored in 20% attrition among participants to arrive at the sample size of 3000.

However, we experienced difficulty in recruiting participants who currently smoke. Recruitment began in September 2022 and concluded in July 2023. In order to address slow recruitment for current smokers, we expanded the recruitment timeline, reached out to over 30 LGBT organizations to canvass over Pride month, flyering ads locally, advertised on social media and on the HER dating app. We further re-opened

the recruitment on the Prolific panel (having enrolled there ~6 months prior) and only received a handful of eligible cases so we ultimately decided to close out the recruitment to focus on the analysis for the remainder of the study.

Figure 1. CONSORT Flow Diagram

Study Protocol

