A. For those who currently smoke

B. For those who did not currently smoke

[figure not shown]
[figure not shown]
The 12 anti-smoking messages were randomly grouped into 4 blocks of 3 messages. The rationale for grouping into 4 blocks of messages is to ensure that the two experimental conditions that will receive the repeated exposures (either 1 message per week or 3 messages per week) would receive unique messages each week without any repetition of messages.

- For participants in the single-message and repeated exposure condition, the 4 blocks of messages were randomly ordered for each week and 1 message from each block was randomly selected, with no repetition, to be shown to the participants each week. These participants saw 4 unique messages over the 1-month period.
- For participants in the 3-message and repeated exposure condition, the 4 blocks of messages were randomly ordered for each week and all 3 messages from each block were shown in random order to the participants each week. These participants saw 12 unique messages over the 1-month period.
- For participants in the other single-message conditions with no repeated exposure, 1 block of messages was randomly selected and 1 message from this block was randomly selected and shown to the participants. These participants viewed only 1 message at baseline.
- For participants in the other 3-message conditions with no repeated exposure and viewed 3 message at baseline, 1 block of messages was randomly selected and 3 messages within this block were shown in random order to the participants. These participants viewed 3 unique messages at baseline.

Two pro-smoking ads were selected from the repository, *Trinkets and Trash*, including a Newport menthol cigarette ad that had been shown in LGBTQ+ magazines and a Natural American Spirit ad that used terms such as “freedom to love” and “freedom to marry” to target LGBTQ+ audiences. One ad was randomly selected to be shown to participants as the threat stimulus. **Figure 3** shows the two pro-smoking ads used in this study.

- For participants in the no-message condition, they did not view any anti-smoking message at baseline. They were shown 1 pro-smoking ad and the post-exposure outcome measures were collected immediately.
- For participants in the single-message and 3-messages immediate conditions, they viewed the anti-smoking messages, followed by the pro-smoking ads, and the post-exposure outcome measures were collected immediately.

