Data analysis plan. We will compare covariate distributions across conditions to evaluate the extent to which randomization was successful. Our main analytic strategy is to fit linear regression models to predict the primary and secondary outcomes immediately after exposure to the pro-tobacco message by experimental condition, stratified by smoking status. This regression-based approach allows us to adjust the effect of message condition for factors that may not have been well balanced by randomization (including baseline values of the outcomes), as well as to explore potential interactions between experimental condition and baseline covariates, which can further inform message development. Let Y_i be the outcome (e.g. intention to quit among smokers) for subject i , x_i be the assigned message condition, and c_i be a vector of individual, meso-, and macro-level covariates. We will fit linear regression models of the form

$$\mathbb{E}(Y_i|x_i, c_i) = \alpha + \beta'x_i + \gamma'c_i$$

where β is a vector of coefficients associated with each treatment condition and γ vector of coefficients associated with the covariates. Each $\hat{\beta}$ is interpretable as the average difference in the outcome immediately after exposure to the pro-tobacco message for that treatment condition, vs. the control condition, adjusting for baseline covariates. All planned comparisons will be tested using two-tailed tests at a Bonferroni-corrected $P<0.05$ cutoff.

To account for differential loss to follow-up by treatment arm, we will apply inverse probability of censoring weighting as follows. For each experimental condition, we will estimate the probability of loss to follow-up at the time of the outcome measurement conditional on covariates using logistic regression. Based on these models, we will generate inverse probability of censoring weights and fit weighted models for the primary and secondary outcomes using a generalized estimating equations (GEE) approach. Under the assumption of Missingness At Random (MAR), these models will yield unbiased and consistent estimates of the treatment effects of interest.

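### The stated outcome model leaves out which of the two randomly selected threat ads each participant saw; adding it is a free improvement, not the repair of an error

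*Combined protocol and SAP*

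**What the plan says.** The section on the ads used states: "Two pro-smoking ads were selected from the repository". One is a menthol ad that had run in LGBTQ+ magazines; the other appeals to LGBTQ+ audiences through wording about freedom in love and marriage. It continues: "One ad was randomly selected to be shown to participants as the threat stimulus". The selection probability is not given, nor whether the draw was balanced within arms. Every arm in Table 1, including the no-message control, meets the threat ad at some point: at baseline, 1 week or 1 month.

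Under Statistical Analyses, linear regressions are to "predict the primary and secondary outcomes immediately after exposure to the pro-tobacco message by experimental condition, stratified by smoking status". The model is alpha + beta'x + gamma'c, "where β is a vector of coefficients associated with each treatment condition and γ vector of coefficients associated with the covariates". The covariates are introduced by letting "c_i be a vector of individual, meso-, and macro-level covariates", and the same section then calls them baseline covariates. The only interactions foreseen come from the intention to "explore potential interactions between experimental condition and baseline covariates". The threat ad is not named as a term, covariate, stratifier or subgroup.

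Two notes under Primary Outcome Measures limit where this matters. Intention to quit (people who smoke) and intention to purchase (both strata) were not collected after the pro-tobacco message in the no-message and the two immediate arms. No such exception is noted for susceptibility or for the secondary outcomes.

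**The concern.** The modelled outcome is the response to a challenge, and the challenge is not the same for everyone. Which ad a person saw is a randomised feature of the stimulus. It is not a baseline characteristic, and in the delayed arms it is shown 1 week or 1 month after baseline, so the covariate vector as described does not contain it.

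Two things follow. Any difference in how strongly the two ads move the outcome stays in the residual variance. And the hypothesis concerns resistance to tobacco marketing in general, while the challenge consists of two ads with different appeals. A single averaged effect cannot show whether protection was similar against both or came mainly from one. The second matter carries more weight, because the plan says that it wants interactions in order to inform message development.

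**Working it through.** **The plan's own figure.** The enrolment section gives a target of 3000 (1500 per smoking stratum), "assuming two-tailed tests, with 80% power", alpha 0.05 and 20% attrition, but no effect size or SD, so 3000 cannot be derived. It can only be back-solved: with 9 equal arms (an assumption), 1500 × 0.8 / 9 = 133 per arm, for which the detectable difference is (1.960 + 0.842) × √(2/133) = 0.34 SD.

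**Inputs.** From the documents: 9 arms; 1075 enrolled who smoke and 1516 who do not; 20% attrition. Assumed: equal allocation, a 50:50 ad split, the same split in every arm, and an ad difference of D residual SDs within ad. The documents give no value for D, so a range is shown.

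- People who smoke: 1075 × 0.8 / 9 = 95.6 per arm, about 48 per arm per ad; detectable arm difference 2.802 × √(2/95.6) = 0.405 SD.
- People who do not smoke: 1516 × 0.8 / 9 = 134.8 per arm, about 67 per arm per ad; detectable arm difference 0.341 SD.

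The figures for people who smoke apply only to secondary outcomes, for the reason in the last step.

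**Precision.** With a 50:50 split the ad adds D²/4 to a within-ad variance of 1. The standard error without the ad term is multiplied by √(1 + D²/4). Power for an effect set to have 80% with the term included becomes Φ(2.802/√(1 + D²/4) − 1.960).

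| D (SD) | 1 + D²/4 | Rise in SE | Power without ad term | Loss (points) |
|---|---|---|---|---|
| 0.1 | 1.0025 | 0.1% | 79.9% | 0.1 |
| 0.2 | 1.0100 | 0.5% | 79.6% | 0.4 |
| 0.3 | 1.0225 | 1.1% | 79.1% | 0.9 |
| 0.5 | 1.0625 | 3.1% | 77.6% | 2.4 |

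If D is measured in raw SDs and baseline covariates explain half the variance, a difference of 0.3 gives 0.0225/0.5 = 0.045 and √1.045 = 1.022, a rise of 2.2%. A split other than 50:50 makes the loss smaller, because p(1 − p) is largest at one half.

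**Type I error.** A simulation of one two-arm contrast (96 per arm, 4000 runs, no arm effect, ad term omitted) rejected in 0.048, 0.051 and 0.047 of runs for D = 0, 0.2 and 0.5, against a nominal 0.05.

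**Chance imbalance in ad share.** Under simple randomisation the SD of the difference in ad share between two arms is √(0.5/n): 0.072 at n = 95.6 and 0.061 at n = 134.8, so 95% ranges of about ±14 and ±12 percentage points. Multiplied by D, the variance this puts into an arm contrast is D² × 0.5/n. The residual-variance calculation adds (2/n) × D²/4, which is the same quantity. It is one loss, and the table already contains it.

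**What a look by ad can show.** Within one ad an arm contrast has variance 4/n, so its 95% half-width is 3.92/√n: 0.40 SD at n = 95.6 and 0.34 SD at n = 134.8. The difference between the two ads has variance 8/n, twice the standard error of the main contrast. The detectable interaction is therefore 2 × 0.405 = 0.81 SD and 2 × 0.341 = 0.68 SD at alpha 0.05. With Bonferroni correction for eight contrasts (the plan does not state the number) it is 1.03 and 0.87 SD.

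**Where the gain applies.** Three of the nine arms, the control among them, have no value immediately after the ad for intention to quit or intention to purchase. No immediate control contrast exists there for an ad term to sharpen. That leaves susceptibility among people who do not smoke and, subject to their having been collected after the ad in all arms, the secondary outcomes in both strata.

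**The case against.** The strongest reply is that nothing here is an error. The ad is randomly selected, an effect averaged over two ads is a legitimate target, and the precision at stake is small and rests on an assumed ad difference. A difference of 0.5 SD between the ads would exceed the arm effect the planned sample could detect (back-solved 0.34 SD), and the outcome items are general rather than about the ad shown, so the lower rows of the table are the more plausible. All of that stands.

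The reply also notes that the anti-smoking messages are randomly drawn, so by the same logic message block would need a term. That part is weaker. Messages belong to the arm's own treatment and are absent in the control, whereas the threat ad is met in every arm and is crossed with all nine.

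It is fair to say that the covariate vector is only loosely defined, so an ad term is unstated rather than excluded. It is also fair that a look by ad could neither confirm nor rule out modest differences. This argues for a descriptive table over a test; it does not argue against looking. Finally, the documents say that Qualtrics delivered the survey and randomised the arms. They do not say that the ad shown was stored, or that it was drawn in the same way in every arm. Both are likely, but they are inferences.

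**Conclusion.** The point holds as a free improvement. The stated model omits a randomised stimulus factor, and agreement of arm effects across the two ads is not examined. The cost in precision is under 1 power point for ad differences up to 0.3 SD and about 2.4 points at 0.5 SD, given a 50:50 split applied alike in all arms.

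A reader might infer more than the documents support:

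- That the arm effects are biased or the tests too liberal. Random selection of the ad rules out the first for effects averaged over the ads, and the simulated error rates show no sign of the second.
- That chance imbalance in ad share is a further harm. It is the same loss seen from another side.
- That the term would repay part of the recruitment shortfall among people who smoke (1075 against 1500) on their primary outcomes. Neither of those outcomes was collected after the ad in the control and immediate arms. That is a separate and larger matter, which an ad term does not touch.

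**What to change.** Add one sentence to the data analysis plan: each model for an outcome collected after the threat ad includes a two-level indicator for the ad shown, in both smoking strata, provided the ad was recorded. Add a second sentence: arm effects against control are tabulated separately for each ad with 95% confidence intervals, labelled descriptive and exploratory. Specify no confirmatory arm-by-ad test, because only differences of roughly 0.7 to 0.8 SD would be detectable. Exclude the control contrasts for intention to quit and intention to purchase from both additions.

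Keep the ad out of the loss-to-follow-up models unless it is known for everyone; in the delayed arms it may have been drawn only when the participant returned. If analysis has already begun, mark both additions as made afterwards.

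The cost is one degree of freedom per model and one table. No new data are needed if the ad shown was stored. If it was not, the plan should say so and state that the effects are averages over the two ads.

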Participants completed the study using the Qualtrics online survey platform. Participants were first screened for eligibility (ages 18-30, identify as sexual minority, and identify as women). We included all individuals who identified as women (cisgender and transgender), as we anticipated that all SMW would be the intended audience of future iterations of ads from this work. Transfeminine populations are currently and traditionally underrepresented in health research, and we did not wish to further marginalize this group by excluding them from participating in this study. Eligible participants completed questions on their baseline outcome measures and characteristics prior to randomization. They were randomly assigned using the Qualtrics built-in randomizer function to one of the nine experimental conditions. **Table 1** provides details of each experimental condition including the sequence of viewing inoculation messages, threat message, and outcomes assessment. We used block randomization to achieve balance across the two conditions based on sexual orientation and race/ethnicity. One month after the baseline survey, participants were invited to complete a follow-up survey to measure the study outcomes and additional questions on participants' characteristics. Depending on the source of enrollment, participants received up to \$12-15 in rewards or gift cards if they completed all phases of the study. The University of Pennsylvania's Institutional Review Board reviewed this study and considered it exempt.

Table 1. Experimental Conditions

No Intervention: No Message Condition

Participants will receive no anti-smoking messages. They will receive the threat message during the baseline survey. Outcomes will be measured before and immediately after seeing the threat message, and at 1 month.

Experimental: Single Message Immediate

Participants will receive a single anti-smoking message followed by the threat message during the baseline survey. Outcomes will be measured before seeing the anti-smoking message and threat message, immediately after seeing the threat message, and at 1 month.

Experimental: Single Message 1 Week Delay

Participants will receive a single anti-smoking message during the baseline survey, followed by the threat message one week later in a separate survey. Outcomes will be measured before seeing the anti-smoking message at baseline, immediately after seeing the threat message at 1 week, and at 1 month.

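### Does the plan need to name its adjustment covariates, including the baseline outcome and the two randomisation factors, in the outcome and censoring-weight models?

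*Combined protocol and SAP*

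**What the plan says.** The Statistical Analyses section fits linear models for the primary and secondary outcomes, separately by smoking status, with terms for message condition and a covariate vector: "c_i be a vector of individual, meso-, and macro-level covariates". The reason given for using regression is that it makes it possible to "adjust the effect of message condition for factors that may not have been well balanced by randomization (including baseline values of the outcomes"). Each treatment coefficient is then interpreted as a difference from control after adjustment for baseline covariates.

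For attrition, the same section fits a model within each experimental condition: "we will estimate the probability of loss to follow-up at the time of the outcome measurement conditional on covariates using logistic regression". The covariates are again not listed. On multiplicity: "All planned comparisons will be tested using two-tailed tests at a Bonferroni-corrected" 0.05 cutoff, with no count of comparisons.

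The Study Protocol section says: "Eligible participants completed questions on their baseline outcome measures and characteristics prior to randomization". It also says: "We used block randomization to achieve balance across the two conditions based on sexual orientation and race/ethnicity". Brief Background, however, says: "Participants were randomized to one of 9 experimental arms using a fractional factorial design".

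**The concern.** Three things look wrong on a first reading.

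- **The covariates are open.** The baseline outcome is usually the strongest predictor of the follow-up outcome, yet it appears only in a parenthesis, as an example of a factor that might be imbalanced. That could be read as adjusting only where imbalance is seen. An open list also leaves room to choose terms after seeing results.
- **The blocking factors are not named in the analysis.** If randomisation was blocked on sexual orientation and race/ethnicity and the model then ignores them, standard errors are too large and tests run below their nominal level.
- **The weights rest on unnamed variables.** The claim of unbiased estimates under missingness at random holds only given what enters the weight models.

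Precision matters here because 1075 smokers were enrolled against 1500 planned. The remedy also looks cheap, since the data were collected before randomisation.

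**Working it through.** **The plan's own figure.** The sample size of 3000 cannot be reproduced, because no effect size, standard deviation or baseline correlation is given. The inputs below marked as assumed are not in the documents.

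**Inputs from the documents.** 9 arms; 1075 smokers and 1516 non-smokers enrolled; 20% attrition; two-sided 0.05; 80% power. *Assumed:* eight arm-versus-control tests, so 0.05/8 = 0.00625; R² = share of the remaining variance explained by the two blocking factors, 2%, 5% or 10%; r = baseline-to-outcome correlation, 0.3, 0.5 or 0.7.

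**1. Blocking factors left out.** The standard error ratio (omitted/included) is 1/√(1−R²). Let z be the two-sided critical value: 1.960 at 0.05, 2.734 at 0.00625.

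- If blocked across the nine arms: actual level = 2[1−Φ(z/√(1−R²))]; power = Φ(z + 0.842 − z/√(1−R²)).
- If not blocked: the level stays nominal; power = Φ((z + 0.842)√(1−R²) − z).

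| R² | SE ratio | Level at 0.05, blocked | Level at 0.00625, blocked | Power at 0.00625, blocked | Power at 0.00625, not blocked |
|---|---|---|---|---|---|
| 2% | 1.010 | 0.0477 | 0.0057 | 79% | 79% |
| 5% | 1.026 | 0.0443 | 0.0050 | 78% | 77% |
| 10% | 1.054 | 0.0388 | 0.0039 | 76% | 74% |

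The departure from nominal level is on the conservative side.

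A simulation with blocked randomisation, per-arm censoring weights and robust standard errors (1075 smokers, 6000 runs) put the level at 0.049, 0.048 and 0.043 with the factors omitted, and at 0.050, 0.053 and 0.053 with them included. The Monte Carlo standard error for one contrast is √(0.05 × 0.95/6000) = 0.0028, so only the 0.043 is distinguishable from 0.05. That simulation assumed no loss in the three arms measured within the baseline survey. Primary Outcome Measures says that neither intention outcome was collected after the pro-tobacco message in those arms, so for smokers the scenario fits only secondary outcomes.

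**2. Baseline outcome left out.** The SE ratio is 1/√(1−r²) = 1.048, 1.155 and 1.400. Power at 0.00625 falls from 80% to 75%, 64% and 43%. These figures describe an omission. The text puts covariates in every model, mentions baseline outcome values among the adjustment factors, and interprets the coefficient as baseline-adjusted.

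**3. How the open wording could be read.** One null contrast, 96 per arm, 20,000 runs, nominal 0.05:

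| Reading | r = 0.3 | r = 0.5 | r = 0.7 |
|---|---|---|---|
| Always adjust | 0.050 | 0.050 | 0.049 |
| Adjust only on significant baseline imbalance | 0.048 | 0.042 | 0.036 |
| Take the smaller p-value of the two models | 0.065 | 0.071 | 0.080 |

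Both readings that the text can support hold the level. The third row is misconduct by selection, which the plan does not propose.

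**4. Cost of fixed terms in the weight models.** Per arm: 1075/9 = 119.4 smokers and 1516/9 = 168.4 non-smokers. At 20% loss that is 23.9 and 33.7 losses. With an assumed 5, 7 or 9 parameters, losses per parameter are 4.8, 3.4 and 2.7 for smokers and 6.7, 4.8 and 3.7 for non-smokers. A fixed set of race/ethnicity and orientation categories could give unstable weights. In arms whose outcome falls within the baseline survey there may be almost no loss to model. In the outcome model the cost is slight: 5 to 9 extra parameters raise variance by about 0.5% to 1.1%.

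**5. The reference to two conditions.** Nine arms are stated in Brief Background, repeated in the description of this experiment, and listed individually in Table 1. The first Project Resist experiment, by contrast, compared tailoring with one control. The wording looks carried over from there, though the documents do not say so. Step 1 gives similar results on either reading.

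**The case for a change.** The strongest case for a change is that a list would take a few sentences and need no new data. It would also remove any doubt about choosing covariates after the fact, which the Bonferroni correction does not cover. The smoker stratum is short of its target. Taking 1500 × 0.8/9 = 133.3 per arm, the planned size implies a detectable effect of 2.802 × √(2/133.3) = 0.343 standard deviations. With 1075 × 0.8/9 = 95.6 per arm, power for that effect at 0.05 is 66% unadjusted and 70%, 78% or 91% adjusted at r = 0.3, 0.5 or 0.7. The Study Protocol also mentions further participant characteristics asked at one month, and nothing in the definition of the covariate vector expressly keeps these out.

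Some of this stands. The list is missing, a named one would be better practice, and the missing-at-random claim cannot be fully checked without it. But the power gain comes from baseline adjustment, which the plan already contemplates. The interpretation of the coefficients refers to baseline covariates, which steers an analyst away from variables measured after randomisation. The protection a list would now give is also limited: recruitment ended in July 2023 and the document is dated July 5 2024, so a list added now might have to be labelled post hoc.

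**Conclusion.** No change to the plan follows. The text lacks detail but makes no wrong choice, and ordinary practice fills the gap: the baseline value of the outcome and the pre-randomisation characteristics go into the model. Omitting the two blocking factors would cause no bias in complete data and would cost 1% to 5% in standard error at an assumed R² of 2% to 10%, with any shift in test level on the conservative side. The heavier figures need either a plain omission of the baseline outcome or selection by p-value, and the text proposes neither. For the weight models, leaving the terms to be chosen with the loss counts in view is a fair trade-off given about 24 smoker losses per arm. The mention of two conditions conflicts with the nine arms and reads as a clerical slip.

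The conclusion rests on the assumed variance shares and correlations, on eight comparisons, and on reading the covariate vector as including the baseline outcome. It would be different if the reported models turned out to omit that term.
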